The study will include all patients 19 years or older who are sampled in the NSQIP Hip Fracture Procedure Targeted Dataset from January 2017 through December 2019 and January to December 2021 undergoing surgical fixation of hip fractures using either general and/or spinal anesthesia. In case of reduced Procedure-Targeted data collection during the COVID-19 pandemic, we will also create a total open hip fracture cohort using relevant *Current Procedural Terminology* codes (27244, 27245, 27269, 27236, or 27248) (20).

Exclusion

Patients with the primary or secondary anesthetic technique listed as local anesthesia alone, local anesthesia with intravenous sedation, epidural, and those with no reported anesthesia technique will be excluded. We will further exclude patients with American Society of Anesthesiologists (ASA) Physical Status (PS) V (defined as “5-Moribund”), and patients with ventilator-dependence preoperatively. Patients with platelet counts $< 80,000/\text{mm}^3$ within 90 days before surgery (21), INR ≥ 1.5 , or PTT > 35 seconds were also excluded for the likelihood of these patients being considered ineligible for SA based on previous guidelines (22, 23).

COVID-19 cohorts

The study will be divided into three cohorts: those undergoing hip surgery 1) without COVID-19 infection January to December 2021, 2) with COVID-19 infection January to December 2021, and 3) pre-pandemic from January 2017 to December 2019.

Due to the variable duration of asymptomatic period that can precede symptoms and diagnosis, COVID-19 infection status will be classified as follows. In our primary analysis, COVID-negative patients will be defined as rows 1 in Table 1, and COVID-positive patients will be defined as row 4. In NSQIP, preoperative COVID status denotes within 14 days before surgery, and patients with preoperative COVID are always coded “No” for postoperative COVID. NSQIP does not have previous history of COVID prior to 14 days, which is a major limitation given the increased mortality of patients with recent COVID undergoing surgery (24).

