As patients with postoperative COVID-positive status are difficult to interpret due to variable incubation period and the possibility of COVID-19 contraction while in hospital post-operatively, we will perform sensitivity analysis using alternative definitions for the COVID-positive cohort, including 1) rows 2, 4, and 6 (i.e. laboratory confirmed preoperatively or post-operatively), 2) rows 4 and 6 (i.e. laboratory confirmed or symptomatic preoperatively), and 3) rows 2, 3, 4, 5, and 6 (i.e. suspected and laboratory confirmed anytime preoperatively or post-operatively).

Table 1

Row #	NSQIP classification	
	Preoperative COVID (within 14 days before surgery)	Postoperative COVID
1	No	No
2	No	Yes – lab confirmed
3	No	Yes – suspected
4	Yes – lab confirmed	No
5	Yes – suspected*	No
6	Yes – suspected	Yes – lab confirmed

*Suspected denotes COVID-19 infection suspected by patient preoperative pneumonia or dyspnea

Outcomes

All outcomes (please see Appendix 1 for detailed definitions) will be measured within 30 days postoperatively, with the exception of length of stay (LOS) which was the total number of days from the day of operation to the day of discharge from hospital (19).

Primary outcomes

The primary outcome is all-cause 30-day mortality following hip fracture surgery.

Secondary outcomes

Secondary outcomes are MI, stroke or cerebrovascular accident (CVA), postoperative delirium, pneumonia, acute renal failure, transfusion, being on ventilator postoperatively (>48 hours), being still in hospital >30 days, length of stay (LOS), discharge destination as home versus not home, hospital readmission, and unplanned reoperation. There will be three composite outcomes: 1) venous thromboembolism (VTE), defined as pulmonary embolism or deep venous thrombosis, 2) sepsis, defined as sepsis or septic shock, and 3) any complication listed above or death. The definitions of secondary outcomes collected from NSQIP variables are included in Appendix 1 (Data Extraction Form).

Exposure

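### The stated rule for coding postoperative COVID conflicts with Table 1 row 6 unless it is limited to lab-confirmed cases; as written, sensitivity definition 2 repeats the primary cohort and definition 1 loses a group its label includes.

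*Combined protocol and SAP*

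**What the plan says.** In Methods, COVID-19 cohorts, the plan gives two facts about the registry. The first is the time window: "preoperative COVID status denotes within 14 days before surgery". The second is a coding rule: "patients with preoperative COVID are always coded" No for postoperative COVID. The rule makes no distinction between lab-confirmed and suspected preoperative infection.

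For the primary analysis, "COVID-positive patients will be defined as row 4", that is, lab confirmed before surgery and No afterwards.

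Table 1 then lists six combinations of preoperative and postoperative code. Row 6 is suspected before surgery and lab confirmed after it. All three alternative definitions of the COVID-positive cohort use this row:

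- Definition 1: "rows 2, 4, and 6 (i.e. laboratory confirmed preoperatively or post-operatively".
- Definition 2: "rows 4 and 6 (i.e. laboratory confirmed or symptomatic preoperatively".
- Definition 3: "rows 2, 3, 4, 5, and 6 (i.e. suspected and laboratory confirmed anytime preoperatively or post-operatively".

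The Statistical Analysis section makes these definitions the first item under sensitivity and exploratory analysis. The Limitations section names misclassification of COVID status as a main limitation.

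**The concern.** The preoperative column of Table 1 treats suspected infection as a Yes level, alongside lab confirmed. A patient in row 6 therefore has preoperative COVID by the table's own coding, and the rule says such a patient is coded No after surgery. Row 6 says the opposite. One of the two statements needs a qualifier or a correction.

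The alternative definitions are the plan's test of whether the result depends on how COVID status is classified. If row 6 cannot occur, one of the three tests returns the primary result under another name, and another does not contain all the patients its label describes. Two analysts working from this text could also build different cohorts.

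**Working it through.** No sample size or power figure is involved. The check lists the six rows of Table 1, applies the coding rule as a filter, and sees what is left of each cohort definition.

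**Inputs (Table 1)**

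| Row | Preoperative | Postoperative |
|---|---|---|
| 1 | No | No |
| 2 | No | Lab confirmed |
| 3 | No | Suspected |
| 4 | Lab confirmed | No |
| 5 | Suspected | No |
| 6 | Suspected | Lab confirmed |

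**Reading A, the rule as written.** Any preoperative Yes implies postoperative No, so a row is possible only if at least one of its two codes is No. Rows 1 to 5 pass. Row 6 is the only row that fails.

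**Reading B, the rule limited to lab-confirmed preoperative cases.** A row is impossible only if it is lab confirmed before surgery and not No afterwards. No row fails, so all six are possible.

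**Each definition under the two readings**

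| Cohort | Rows listed | Reading A | Reading B |
|---|---|---|---|
| Primary | 4 | 4 | 4 |
| Definition 1 | 2, 4, 6 | 2, 4 | 2, 4, 6 |
| Definition 2 | 4, 6 | 4 | 4, 6 |
| Definition 3 | 2, 3, 4, 5, 6 | 2, 3, 4, 5 | 2, 3, 4, 5, 6 |

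**What follows under reading A**

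1. Definition 2 contains the same patients as the primary cohort. The same model on the same patients gives the same odds ratio and P value, apart from simulation noise if multiple imputation is run afresh.
2. A patient suspected before surgery and confirmed afterwards would carry the codes suspected and No, which is row 5. Definition 1 does not list row 5, so it leaves out a patient who was lab confirmed postoperatively and whom its label includes. This step is inferred from the rule; the text does not describe how such a patient is coded.
3. Definition 3 lists row 5, so it keeps that patient.

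**Definition 2's label under either reading.** The label covers patients who were symptomatic before surgery. The footnote to row 5 explains suspected as preoperative pneumonia or dyspnea, so row 5 fits the label, yet it is not listed. With row 5 added, definition 2 becomes rows 4 and 5 under reading A and rows 4, 5 and 6 under reading B. Both differ from the primary row list.

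**The case against.** The strongest reply is that the rule was meant only for lab-confirmed preoperative cases. It comes directly after the sentence defining the primary cohort as row 4, and can be read as explaining why row 4 shows No after surgery. Table 1 fits this: lab-confirmed preoperative infection is paired only with No, while suspected infection appears both with No and with lab confirmed. On this reading all six rows are consistent and the defect is one missing qualifier. That reading is plausible and cannot be excluded. It is not stated, however, and Appendix 1, which might settle it, is not in the text reviewed.

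A second reply is that adding row 5 to match definition 2's label already separates it from the primary cohort, whether or not row 6 is empty. That is right for definition 2. It leaves the conflict between the rule and row 6 in place, and it does nothing for definition 1.

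A third reply is that the harm would show itself, because definition 2 would have the same number of patients and deaths as the primary analysis. That is likely, but a replacement definition chosen at that stage would be post hoc.

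A reader might also infer that row 6 is certainly empty, or that definition 2 would be almost uninformative even if row 6 held a few patients. The documents support neither. Whether row 6 occurs is a fact about the registry that they leave open, and they give no row counts. Moreover, a small added group does not by itself make a misclassification check empty; what matters is whether those patients shift the estimate.

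**Conclusion.** The point holds in a conditional form. The coding rule and row 6 contradict each other unless the rule is limited to lab-confirmed preoperative cases, and the documents do not say which applies.

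If the rule holds as written, row 6 has no patients, definition 2 overlaps the primary cohort completely, and definition 1 reduces to rows 2 and 4. The loss of patients suspected before and confirmed after surgery from definition 1 rests on the further inference that they are coded as row 5. If the narrower rule applies, neither consequence arises, and what remains is a missing qualifier and the mismatch between definition 2's rows and its label.

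Because all three definitions cite row 6, a reader might infer that all three fail, or that the main result is in doubt. Neither follows. Definition 3 keeps the affected patients through row 5, definition 1 still differs from the primary row list through row 2, and the primary analysis uses only row 4. The problem is confined to the sensitivity analyses. It is worth correcting because it decides which patients enter a prespecified check on a limitation the plan itself names.

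**What to change.** Before any outcome model is fitted, cross-tabulate every preoperative code against every postoperative COVID code for the 2021 patients. Include combinations Table 1 does not list, such as suspected at both times, which the narrower rule would allow. Then reconcile the COVID-19 cohorts text with Table 1.

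- **If row 6 is empty:** delete it from the table and from all three definitions. Define definition 2 as rows 4 and 5, which matches its label. State that definition 1 cannot capture patients suspected before surgery and confirmed after it.
- **If row 6 occurs:** limit the coding rule to lab-confirmed preoperative cases, and add row 5 to definition 2 (rows 4, 5 and 6) so that its row list agrees with its label.

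The cost is one cross-tabulation and a short wording correction, with no new data. Made before outcomes are examined, the change keeps the sensitivity definitions prespecified.

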The exposure to either SA or GA will be modelled as a binary variable (please see Appendix 1 for detailed definitions). SA will be defined as having either spinal or managed anesthesia care (MAC) documented the primary anesthesia technique, without GA secondary anesthesia technique. In NSQIP, regional anesthesia with MAC would be coded as MAC for the principal technique. Since it is highly unlikely that patients can tolerate hip fracture repair under sedation alone, MAC is counted as SA for the analysis. Those receiving both SA and GA (presumably either failed spinal and/or conversion to GA for other purposes) will be excluded from the primary analysis, but included in *a priori* sensitivity analysis with cohort characteristics displayed as a third comparison group, and analyzed as part of the GA group for the multivariable logistic regression.

Confounders

We selected an *a priori* list of potential confounders to adjust for the choice of anesthetic technique, based on availability within NSQIP, literature, clinical experience, and consensus within our multidisciplinary team. The confounders are: age, sex, race, body mass index (BMI) (calculated from height and weight in NSQIP), American Society of Anesthesiologists (ASA) Physical Status (PS), smoker within one year preoperatively, severe obstructive chronic pulmonary disease (COPD), dyspnea, coagulopathy (bleeding disorders), congestive heart failure (CHF), hypertension on medications, preoperative renal failure (acute renal failure, dialysis, and/or GFR < 60 mL/min/1.73 m² based on preoperative creatinine) (25), diabetes, preoperative functional status, preoperative delirium or dementia, systemic sepsis, total operating time, and days from hospital admission to operation. The definitions of potential confounding variables collected from NSQIP variables are included in Appendix 1 (Data Extraction Form). Since some of the potential confounders may provide similar information, collinearity will be assessed and variables will be combined or eliminated as described in the statistical analysis plan below.

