3. Sample size calculated based on R-squared (variance explained by the multi-variable logistic regression) and mortality difference between SA vs. GA (Table 2). Assumptions are: alpha = 0.05, baseline mortality rate 36%, ratio of SA:GA of 1:4. For example, with approximately 500-1000 patients from NSQIP, the study would likely be able to detect a 12 to 14% mortality difference depending on the R-squared.

Table 2. Sample size calculation for logistic regression using G*Power software.

Amount of R ² accounted for by covariates	Detectable difference in mortality			
	8%	10%	12%	14%
0.1	1820	1139	771	552
0.2	2048	1281	868	621
0.3	2340	1464	992	709
0.4	2730	1708	1157	827

1.

Data will be analyzed using R. Significance level will be set at P <0.05.

List of variables in cohort characteristics include but are not limited to (Please see Appendix 1 for details)

Patient characteristics: Age, sex, race, body mass index (BMI) (calculated from height and weight in NSQIP), American Society of Anesthesiologists (ASA) Physical Status (PS), smoker within one year preoperatively, severe obstructive chronic pulmonary disease (COPD), dyspnea, coagulopathy, congestive heart failure (CHF), hypertension on medications, preoperative renal failure (acute renal failure, dialysis, and/or GFR < 60 mL/min/1.73 m² based on preoperative creatinine) (25), diabetes, ascites, preoperative functional status, preoperative dementia/delirium, systemic sepsis, preoperative use of mobility aid, and preoperative pressure sore.

Surgical factors: Total operating time, year of surgery, hip fracture type, pathological fracture, and days from hospital admission to operation.

Systems factors: Medical co-management, and participation in a standardized hip fracture care program.

Postoperative variables:

- Mortality
- Myocardial infarction
- Stroke/CVA
- Postoperative delirium
- VTE (composite: pulmonary embolism, DVT)
- Pneumonia
- On ventilator >48h postoperatively
- Acute renal failure
- Sepsis or septic shock (composite of systemic sepsis and septic shock)
- Transfusion (packed red blood cell (PRBC) within the first 72 hours of surgery start time)
- Readmission: also present % unplanned
- Unplanned reoperation
- Still in Hospital > 30 Days
- Non-home discharge
- Weight bearing as tolerated (WBAT) on postoperative day (POD) #1
- Wound issues (composite: superficial and deep infection, wound disruption)
- New postoperative pressure sore
- Urinary tract infection

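### The discharge-destination and transfusion models have no baseline for prior residence or for preoperative hematocrit/hemoglobin, and the plan fixes one covariate set for every secondary outcome.

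*Combined protocol and SAP*

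**What the plan says.** Under Outcomes, Secondary outcomes, the plan includes "length of stay (LOS), discharge destination as home versus not home, hospital readmission, and unplanned reoperation". The list of postoperative variables repeats the discharge item as "Non-home discharge", with no qualifier about where the patient lived before the fracture. It defines the transfusion outcome as "Transfusion (packed red blood cell (PRBC) within the first 72 hours of surgery start time".

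The Confounders section enumerates the adjustment set. It opens with "The confounders are: age, sex, race, body mass index (BMI) (calculated from height and weight in NSQIP" and closes with "preoperative functional status, preoperative delirium or dementia, systemic sepsis, total operating time, and days from hospital admission to operation". I count 18 items. Functional status and delirium or dementia are there, and so is "coagulopathy (bleeding disorders), congestive heart failure (CHF), hypertension on medications". Prior residence, hematocrit and hemoglobin are not.

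Statistical Analysis, item 3, uses the same independent variables in all secondary-outcome regressions. The list of cohort characteristics is expressly open-ended. Its named patient items end with "diabetes, ascites, preoperative functional status, preoperative dementia/delirium, systemic sepsis, preoperative use of mobility aid, and preoperative pressure sore", again without prior residence or a red-cell measure.

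The plan already relies on preoperative laboratory values. The Exclusion section uses platelet count, and patients with values "within 90 days before surgery (21), INR ≥ 1.5 , or PTT > 35 seconds were also excluded"; the renal-failure confounder uses creatinine. Detailed definitions of outcomes and confounders are referred to Appendix 1, which is not in the supplied text.

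**The concern.** Each of these two outcomes needs a baseline to be interpretable. A patient who lived in a nursing facility and returns there has regained the prior residence, yet on the body text is scored not home whichever anesthetic was given. Such patients carry almost no information about the effect of technique on recovery. If they are spread unevenly over SA and GA, they create a difference that has nothing to do with technique. Functional status and dementia are only partial stand-ins for residence.

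Transfusion raises the same issue. A patient who enters the operating room with a low hematocrit plausibly starts closer to being transfused. Coagulopathy describes bleeding tendency and is not a red-cell measure.

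Morbidity is the plan's stated secondary objective, and the Limitations section relies on multivariable adjustment to mitigate confounding by indication, so the content of the covariate list matters. The composite of any listed complication or death does not say whether discharge destination and transfusion count towards it, so the problem may reach the composite too.

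**Working it through.** **The plan's own figure.** The plan states no numbers for discharge or transfusion. The nearest stated figure is the covariate budget in the sample size section: 100 + 50i with about 1000 patients. With i = 18, 100 + 50 × 18 = 1000, which matches the 18 variables stated and the 18 confounders listed. Counting the SA/GA exposure as well gives i = 19 and 1050.

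**Discharge: imbalance in prior residence.** The documents give no facility share or discharge rate, so every input is assumed: 97% not home among prior facility residents, 60% among those from home, no effect of technique. With facility share f, P(not home) = 0.97f + 0.60(1 − f).
- f = 0.20 (SA): 0.194 + 0.480 = 0.674; odds 0.674/0.326 = 2.07.
- f = 0.30 (GA): 0.291 + 0.420 = 0.711; odds 0.711/0.289 = 2.46.
- Crude odds ratio: 2.07/2.46 = 0.84. With the shares reversed it is 1.19. With equal shares, or among patients admitted from home only, it is 1.00.

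The plan reports an adjusted estimate, so what matters is the imbalance left after adjustment. On the same assumed rates:

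| Facility share, SA vs GA (assumed) | P(not home), SA vs GA | Odds ratio with no effect |
|---|---|---|
| 20% vs 30% | 0.674 vs 0.711 | 0.84 |
| 22.5% vs 27.5% | 0.683 vs 0.702 | 0.92 |
| 24% vs 27% | 0.689 vs 0.700 | 0.95 |
| equal | equal | 1.00 |

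**Discharge: dilution without imbalance.** Assume 60% of GA patients from home go elsewhere, a true SA odds ratio of 0.70 among patients from home, and all facility residents scored not home. The SA odds are 0.70 × 1.5 = 1.05, so the SA risk is 0.512. Mixing in a facility share f in both groups:
- f = 0.10: 0.561 vs 0.640, odds ratio 0.72, risk difference −7.9 points.
- f = 0.20: 0.610 vs 0.680, odds ratio 0.74, −7.0 points.
- f = 0.30: 0.659 vs 0.720, odds ratio 0.75, −6.1 points.

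The undiluted risk difference is −8.8 points.

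**Transfusion: imbalance in anemia.** The inputs are again assumed. For anemia with risk ratio RR and prevalence a (SA) and b (GA), the spurious crude risk ratio is [1 + a(RR − 1)] / [1 + b(RR − 1)].
- RR = 3, 30% vs 40%: 1.6/1.8 = 0.89.
- RR = 5, 30% vs 40%: 2.2/2.6 = 0.85.
- Equal prevalence: 1.00.

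The odds ratio would move in the same direction.

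**Effect of the fix on size.** Restricting the discharge model to patients from home leaves about 900, 800 or 700 of 1000 if 10%, 20% or 30% are facility residents (assumed). One extra covariate in the transfusion model gives 100 + 50 × 19 = 1050, or 1100 with the exposure counted, against about 1000 expected.

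**The case against.** The strongest reply has five parts.

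- **Appendix 1.** A reader might infer that returning facility residents will certainly be counted as bad outcomes. The documents do not establish that. Outcome definitions are placed in Appendix 1, which could treat a prior facility as home. This stands for the coding of discharge. It does not extend to the covariates: the confounder list is given in the body, and the appendix is cited only for definitions.
- **Main predictor.** A reader might also infer that each model omits its main predictor. Nothing in the documents ranks predictors of discharge or transfusion, so that claim is unsupported. A predictor biases the comparison only if it also differs between SA and GA.
- **Crude figures.** The 0.84 is unadjusted and rests on assumed inputs. Adjustment for age, ASA status, functional status and dementia would shrink it. It is also about one standard error: with 200 SA and 800 GA patients, SE(log OR) = √[1/(200 × 0.674 × 0.326) + 1/(800 × 0.711 × 0.289)] = 0.17, and log 0.84 = −0.17. The dilution is modest too. All of this stands.
- **Existing provisions.** The plan includes an E-value, acknowledges missing confounders and names confounding by indication as a limitation. These describe residual confounding but do not replace a baseline covariate, and the examples of missing confounders concern COVID severity.
- **Budget.** The 18 listed confounders already exhaust the plan's own rule at 1000 patients. This is a real cost, but it does not justify leaving the omission unmentioned. The open-ended wording of the cohort list does not help either, because it governs the descriptive tables and not the models.

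**Conclusion.** The concern holds in a limited form. As the body text stands, the discharge model ignores prior residence, the transfusion model ignores preoperative hematocrit or hemoglobin, and the single covariate set prevents either from entering only the model that needs it. The consequence for discharge is conditional on Appendix 1 not coding return to a prior facility separately.

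The size is unknown from the documents. On assumed inputs, a 10-point imbalance in prior residence gives a crude odds ratio of 0.84 or 1.19 with no true effect, and 0.92 to 0.95 if adjustment leaves a gap of 5 to 3 points. An assumed 10-point imbalance in anemia gives a crude risk ratio of 0.85 to 0.89. With no residual imbalance there is no bias, only dilution of the discharge contrast. The direction cannot be predicted. Only secondary outcomes, and possibly the composite, are touched; the primary mortality analysis and its sample size are not. The plan should be changed on this point before the data are analyzed.

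**What to change.** - **Discharge.** State how return to a prior facility is coded, and fit the model in patients admitted from home. If the dataset does not hold prior residence, report discharge destination descriptively and draw no SA-GA conclusion from it.
- **Transfusion.** Permit outcome-specific covariates in Statistical Analysis, item 3, and add preoperative hematocrit or hemoglobin as a continuous term in this model, subject to the missing-value rules under Preprocessing. If those rules remove it, say so beside the transfusion result.
- **Cohort table.** Show prior residence and hematocrit or hemoglobin by SA and GA, so that readers can see any imbalance.
- **Composite.** State whether discharge destination and transfusion count in it.

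The cost is two more extracted variables and a few sentences. The discharge model becomes smaller, at about 700 to 900 of 1000 patients on the assumed facility shares. The transfusion model goes one covariate beyond the 100 + 50i rule (1050 against about 1000), which the plan should acknowledge. That the dataset holds both fields is an assumption; the documents say only that it has more than 150 clinical variables.
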